## **9. EVALUATION OF ADVERSE EVENTS**

### **9.1. Evaluation of Liver Graft-Related Adverse Events (LGRAEs)**

Liver Graft-Related Adverse Events (LGRAEs) are those which have any untoward effect on the health or safety of the patient and that are related to the transplanted liver function (except for acute rejection). LGRAEs will be collected from the time a subject is transplanted with a liver preserved on OCS until the completion of the 30-day follow-up evaluation. A LGRAE will be followed until resolution or stabilization of the event.

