## 9.5. Recording and Reporting of Adverse Event

All liver graft-related adverse events and serious adverse events are to be captured until post-transplant day 30 or until initial hospital discharge, whichever comes first. The description of the adverse event will include: the date of onset, duration, severity, seriousness, the relationship of the event to the trial treatment, anticipated or not, and any treatment required. All liver graft-related serious adverse events occurring during the course of the first 30 days post-transplant will be reported to TransMedics, Inc., as well as documented on the appropriate electronic case report form(s). For all liver graft-related SAEs, the investigator is required to supply any additional data that may be deemed necessary by the Sponsor. Additionally, any serious adverse events (SAE) and unanticipated adverse device effects (UADE) should be reported to TransMedics, Inc., as soon as possible after the investigator learns of the event. LGRAEs will be recorded up to the 30-day follow-up or through hospital discharge only if longer than 30 days. For any particular patient, the CEC, if required to protect patient safety, may specify a different follow-up period. The Sponsor is responsible for the classification and reporting of liver graft-related adverse events to the appropriate regulatory authorities, and for the on-going safety evaluation of the trial in accordance with ISO 14155 and governing regulatory requirements.

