## 9.6. Relationship of an Adverse Events (AEs) to OCS Liver System

The investigator will assess the relationship of the Adverse Event (AE) to the OCS Liver System. The relationship will be assessed using the following categories:

- **Definitely Related:** There is a reasonable causal and temporal relationship between preservation with the OCS Liver System and the adverse event.
- **Probably Related:** It is more likely than not that there is a reasonable causal relationship between preservation with the OCS Liver System and the adverse event.
- **Unlikely Related:** There is a temporal relationship with preservation with the OCS Liver System and the adverse event, but there is not a reasonable causal relationship between the trial device and the event.
- **Unrelated:** There is no relationship between preservation with the OCS Liver System and the adverse event.

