### 10.4. Analysis of Safety

Safety will be analyzed principally by examination of the frequency of liver graft-related serious adverse events (SAEs) up to the 30-day follow-up after transplantation. This endpoint is defined as the average number of liver graft-related serious adverse events through the 30 days post-liver transplantation per subject, consisting of the following serious adverse events (at most one per type per person):

- Primary non-function (defined as irreversible graft dysfunction requiring emergency liver re-transplantation or death within the first 10 days, in the absence of immunologic or surgical causes)
- Ischemic biliary complications (ischemic biliary strictures, and non-anastomotic bile duct leaks)
- Vascular complications (liver graft-related coagulopathy, hepatic artery stenosis, hepatic artery thrombosis and portal vein thrombosis)
- Liver allograft infections (liver abscess, cholangitis, etc.).

In addition, the numbers and percentages of subjects experiencing at least one liver graft-related AE, at least one (definitely or probably-related) device-related AE, at least one unanticipated AE, and at least one serious AE, and the number and percentage of deaths will all

be tabulated. Also, the number of liver graft-related adverse events and the number and percentage of subjects experiencing liver graft-related adverse events will be tabulated by system organ class and preferred term using MedDRA. A similar analysis will be performed for LGRSAEs. AEs will also be tabulated at the event level by system organ class and preferred term and the relationship of the adverse event to the device using counts and percentages. Similar analyses will be performed by the severity of the adverse event.

For livers that are not transplanted, the reason(s) for non-transplantation (including device failure) will be summarized using counts and percentages. The number and percentage of donor livers in the Donor Liver Population for which these was a device failure will also be presented.

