## APPENDIX 2. SCHEDULE OF CLINICAL ASSESSMENTS

Evaluations	
Eligibility & ID	X
Demographics/Characteristics	X
Donor Cause of Death	X
Donor Medical & Social History	X
Donor Liver Assessment	X
Donor Cross Clamp Time and Flush Detail	X
Post-Preservation Liver Biopsy and if applicable Bile duct specimen	X
OCS Preservation Parameters	X
OCS Liver Enzymes & Lactate Levels	X
Device Malfunction (if applicable)	X
Non-transplant Reasons (if applicable)	X

Evaluations	Recipient Schedule of Assessments					
	Tx. Day - Day 7 Post-Tx.	Discharge	Day 30	Month 6	Month 12	Month 24
Eligibility & Informed Consent	X					
Demographic/Characteristics	X					
Medical & Risk Factors	X					
Transplant Details	X					
Early Liver Allograft Dysfunction (EAD) Surveillance	X					
Mechanical Ventilator Support	X					
Patient Survival	X	X	X	X	X	X
Graft Survival	X	X	X	X	X	X
Immunosuppressive Meds & Induction (if applicable)	X	X				
Initial ICU & Hospital Stay	X	X				
Liver graft-related (AE's & SAE's)	X	X	X	X		
Liver graft-related re-hospitalizations				X	X	
Ischemic biliary complications				X	X	
Liver Biopsy *	X				X	X

\* ONLY tests regularly scheduled per center standard of care or performed due to a clinical cause at these timepoints will be collected.

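### The device-related and unanticipated AE rows in section 10.4 are wider than the graft-related events that the protocol routinely collects, so they may undercount, chiefly non-serious events outside graft function

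*Combined protocol and SAP*

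**What the plan says.** **Tables.** Section 10.4 lists a row for subjects with a liver graft-related AE, followed by separate rows for subjects with "at least one (definitely or probably-related) device-related AE, at least one unanticipated AE, and at least one serious AE". It also plans an event-level table of AEs by relationship to the device.

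**Collection.** Section 9.1 states that "LGRAEs will be collected from the time a subject is transplanted with a liver preserved on OCS", up to the 30-day evaluation. It defines these events as "related to the transplanted liver function (except for acute rejection"). The only AE row in the recipient schedule of Appendix 2 is "Liver graft-related (AE's & SAE's").

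**Recording and reporting.** Section 9.5 opens with "All liver graft-related adverse events and serious adverse events are to be captured". It then says "All liver graft-related serious adverse events occurring during the course of the first 30 days post-transplant will be reported to TransMedics, Inc" and documented on the eCRF. Later it adds that "any serious adverse events (SAE) and unanticipated adverse device effects (UADE) should be reported to TransMedics, Inc., as soon as possible". Section 14.2 requires the sponsor to be told of every subject death. Section 9.2 limits follow-up to resolution to graft-related SAEs.

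**Causality.** Section 9.6 has four levels: Definitely, Probably, Unlikely and Unrelated. Unlikely applies where timing fits but "there is not a reasonable causal relationship between the trial device and the event".

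**The concern.** Section 10.4 treats graft-related AEs as one row among several, so a reader will take the device-related and unanticipated rows to cover all AEs of those kinds. The collection rules select on a different attribute: whether the event concerns the function of the transplanted liver. An event can be caused by preservation on the device without concerning graft function. The perfusate in section 7.4 contains packed red cells, heparin and antimicrobials, and the anticipated-event list in section 9.3 includes transfusion reaction and heparin-induced thrombocytopenia. Neither need be related to liver function.

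Section 1 says this protocol gathers further clinical data while the marketing application is prepared and reviewed. A row titled device-related AE would naturally be read as complete. The formal SAP is still to be finalised (section 10.6). It can retitle a row, but it cannot recover events that were never collected.

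**Working it through.** The documents give no AE rate, precision or power for these tables, so there is no figure to reproduce. The check compares what is tabulated with what is collected.

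**Step 1: route into the data by type of event**

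| Type of event | Row in 10.4 | Stated route |
|---|---|---|
| Graft-related, serious or not | Graft-related, and others as judged | 9.1, 9.5, Appendix 2 row |
| Not graft-related, serious | Serious; device-related or unanticipated if so judged | Report to sponsor (9.5); UADE (9.5, 14.2); deaths (14.2). eCRF entry not stated |
| Not graft-related, non-serious, device-related | Device-related | None found |
| Not graft-related, non-serious, unanticipated | Unanticipated | None found |

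The last two lines are the gap. The unanticipated-AE definition in section 9.3 turns on association with the device, and its opening limb is not confined to serious events. The UADE definition in section 9.4 is confined to serious ones. The UADE route therefore covers the serious part of the unanticipated row and leaves the non-serious part uncovered.

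**Step 2: serious events.** The reporting duty in section 9.5 covers any SAE. The explicit eCRF instruction in 9.5 and the Appendix 2 row name graft-related SAEs only. The opening sentence of 9.5 can be read as all SAEs or as graft-related SAEs. So a report exists, but the documents do not say that it reaches the database from which the table is built.

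**Step 3: capture window.** One sentence of 9.5 ends capture at the earlier of Day 30 and discharge. Another runs to Day 30, or to discharge if that is later. Section 9.1 uses the 30-day evaluation. Under the earlier-of rule, non-serious events between an early discharge and Day 30 would also be lost.

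**Step 4: causality scale.** Take an event with a reasonable but less than 50% chance of device cause and a fitting time course.
- Probably: not met, because it needs a relation that is more likely than not.
- Unlikely: not met, because it needs the absence of a reasonable causal relation.
- Definitely: met if read literally, because its definition asks only that the causal and temporal relation be reasonable.

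An investigator could follow the literal definition upwards or the label downwards. The categories are not cleanly ordered or exhaustive, and the direction of misclassification is unknown.

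**Step 5: scale, by assumption only.** Let n = 184 (section 10.5) and let c be the fraction of affected subjects who are captured. The documents give no value for c; 0.75 and 0.5 are assumed.
- True subject rate 10%: expected 184 × 0.10 = 18.4. Tabulated 18.4 × 0.75 = 13.8 (7.5%) or 18.4 × 0.5 = 9.2 (5.0%).
- No subject seen: two-sided 95% upper bound 1 − 0.025^(1/184) = 1.98% with full capture. For the true rate, dividing by c gives 2.65% (c = 0.75) or 3.97% (c = 0.5).
- True rate 1%: chance of seeing none is (1 − 0.01c)^184 = 15.7% (c = 1), 25.0% (c = 0.75) or 39.8% (c = 0.5).

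**The case against.** The strongest reply has four parts.

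1. *Serious events are covered.* Section 9.5 asks for any SAE and any UADE, and section 14.2 for every death. The follow-up limit in section 9.2 restricts follow-up, not capture, and makes most sense if other SAEs are recorded too. A missing schedule row does not cancel a reporting duty. This stands. A reader might infer that the serious-AE row must undercount; the documents do not support that. What remains is that eCRF entry of non-graft SAEs is not stated.

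2. *The causality scale does not push one way.* A reader might infer that reasonable but less-than-likely events default to Unlikely and drop out of the device-related row. No such default appears, and Definitely can literally take them. This also stands. In addition, the event-level table shows every relationship category, so events coded Unlikely remain visible, although that table cannot separate borderline cases from implausible ones.

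3. *The uncovered set may be small.* Seriousness in section 9.2 includes prolonged hospitalisation, so many in-hospital events would qualify as SAEs. Device malfunctions are recorded and device failures tabulated separately. This limits the size, which is unknown, but does not close the gap.

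4. *AE in section 10.4 may simply mean the AEs collected.* That is possible, but 10.4 lists graft-related AEs as their own row beside the others. If the narrower meaning is intended, the row titles should say so.

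**Conclusion.** The point holds for two rows. If the protocol is followed as written, the device-related and unanticipated AE rows may undercount, chiefly by missing non-serious events outside graft function. This rests on reading those rows as not confined to graft-related events, as the layout of section 10.4 indicates, and on the absence of any other collection instruction in the document. The amount cannot be estimated from the documents; the figures above show scale under assumed capture only.

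For the serious-AE row, unclear database capture is the finding, not an undercount. For the causality scale, the finding is loose definitions with error of unknown direction. It would go too far to say that the two problems together make the device look safer.

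The consequence is confined to descriptive secondary safety tables in a single-arm study. The principal safety endpoint is itself built from liver graft-related SAEs through 30 days and is not affected by the scope or causality points.

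**What to change.** - **Collection.** In sections 9.1 and 9.5 and Appendix 2, require eCRF entry of any AE judged device-related or unanticipated, whether or not graft-related. State that all SAEs through Day 30 are entered.
- **Or titles.** If collection is not widened, retitle the section 10.4 rows to the scope actually collected, that is, liver graft-related events.
- **Reconciliation.** Bring 9.1, 9.2, 9.5 and Appendix 2 into agreement on which events are recorded and over what window.
- **Causality.** Reword the section 9.6 categories so that they are ordered and exhaustive. Adding a middle level, with the device-related row shown both with and without it, is one way. Whether that keeps comparability with the parent PROTECT study cannot be checked here, because that study's scale is not in the documents, and a new level could draw events out of Definitely or Probably.

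**Cost.** A modest increase in AE entry at sites if collection is widened, and no added site burden if the rows are only retitled. Widened collection has to be in place while subjects are being followed, whereas retitling can wait for the SAP.

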## 10.5. Sample Size Determination

The sample size for this CAP was determined based on the rate of enrollment in the PROTECT trial. The maximum number of patients enrolled is 184.

## 10.6. Statistical Analysis Plan

A formal statistical analysis plan will be prepared and finalized prior to data lock.

## 10.7. Stopping Rule

The following stopping rule is to be used in the study:

- Stopping Rule: Let  $p$  denote the true proportion of recipients transplanted with an OCS-preserved liver for whom the recipient does not survive until Day 30. Whenever a recipient dies within 30 days post-transplant, calculate a 97.5% lower confidence bound for  $p$ . Stop the study if this lower confidence bound exceeds 0.15 (15%).

**Table 1** below shows the conditions under which the study would be stopped for a range of number of deaths ( $m$ ) and a range of number of recipients ( $n$ ). (The above stopping rule would, however, be applied to all combinations of number of deaths and number of recipients that were observed in the study.) The word “Stop” in a cell indicates that the study would be stopped if this condition were met. If the word “Continue” appears, the study would continue. A dash indicates an impossible condition, with  $m > n$ . One sees, for example, that the study would be stopped if there were 4 deaths out of the first 5 recipients or 5 deaths out the first 10 recipients.

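### The mortality stopping rule in Section 10.7 does not say how recipients still short of Day 30 enter n; its natural reading counts them as survivors, which lowers the bound and can delay stopping

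*Combined protocol and SAP*

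**What the plan says.** Section 10.7 defines p as the true proportion of recipients of an OCS-preserved liver "for whom the recipient does not survive until Day 30". The trigger and the calculation are given in one instruction: "Whenever a recipient dies within 30 days post-transplant, calculate a 97.5% lower confidence bound for" p; the study stops if that bound is above 0.15. Table 1 lays out the decision by number of deaths (m) and number of recipients (n). The text adds that the rule "would, however, be applied to all combinations of number of deaths and number of recipients that were observed in the study", and gives as examples that "the study would be stopped if there were 4 deaths out of the first 5 recipients or 5 deaths out the first 10 recipients".

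The section does not define n at a look, mention recipients with less than 30 days of follow-up, or pause enrolment. It does not name the interval method. Section 10.5 says "The maximum number of patients enrolled is 184" and refers to the PROTECT enrolment rate without giving a figure. Under Section 10.7 the sponsor applies the rule and the DSMB reviews it at scheduled meetings. Section 10.6 requires the statistical analysis plan only before data lock, which is too late to govern a rule applied during enrolment.

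**The concern.** The quantity monitored is a Day-30 outcome, but the looks happen at deaths, while enrolment continues. At most looks some recipients will be alive with only part of their 30 days observed. Putting all of them in n with no event treats each as a Day-30 survivor. The estimate of p is then too low and so is its lower bound.

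The opposite shortcut is also biased. If n is deaths plus those who have reached Day 30, every early death counts at once while the survivors transplanted alongside it are left out until later, so mortality is overstated.

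This is the only numerical stopping boundary in the protocol. How quickly it acts should be settled in the text and not by whoever computes n at the time.

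**Working it through.** **1. Reproduce Table 1.** The exact (Clopper-Pearson) one-sided 97.5% lower bound for m deaths in n is the 2.5% quantile of a Beta(m, n − m + 1) distribution.

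| m/n | Bound | Decision at 0.15 |
|---|---|---|
| 3/5 | 0.147 | continue |
| 4/5 | 0.284 | stop |
| 4/10 | 0.122 | continue |
| 5/10 | 0.187 | stop |

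These match the n = 5 and n = 10 rows and both worked examples. Wilson, Wald and the exact one-sided 95% bound all stop at 3/5, so they do not fit the table. The n = 20 row is incomplete in the text available to me and nothing rests on it.

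**2. One set of data, three denominators.** Suppose 20 recipients have been transplanted: 6 have died, 7 are alive past Day 30, and 7 are alive with 10 days of follow-up on average.

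- All recipients: n = 20, bound 0.119, continue.
- Weighted by follow-up: n = 6 + 7 + 7 × 10/30 = 15.33, bound 0.159, stop.
- Deaths plus completers: n = 6 + 7 = 13, bound 0.192, stop.

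The example sits near the boundary: under n = 20, a seventh death gives 0.154 and stops the study.

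**3. Dilution in terms of deaths.** With 20 recipients of known status, 7 deaths stop the study. Adding 5, 10 or 20 pending recipients as survivors (n = 25, 30, 40) raises the requirement to 9, 10 or 12 deaths.

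**4. Size of the delay (simulation).** From the documents: maximum 184 recipients, a look at each death within 30 days, 97.5% level, 15% threshold. Assumed: random arrivals at 8, 15 or 25 a month; deaths either even over 30 days or front-loaded (mean about 8 days). Each simulated trial was run under both denominators and the difference taken within the trial. At a true mortality of 25%, the weighted n stops earlier than n = all recipients by:

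- 8 a month: median 2–3 transplants
- 15 a month: median 8
- 25 a month: median 21–23

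Mean savings over these settings run from about 10 to 37, because a minority of trials are delayed a long way. The chance of ever stopping is 94–96% with all recipients and 95–99% with weighting. A separate run at 5–20 per 30 days and 25–40% mortality gave medians of 0–14 and means of 1–26.

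**5. The weighted n is not a neutral yardstick.** Take recipients 10 days after transplant, true mortality 25%.

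- Front-loaded deaths: about 0.18 expected deaths each; expected weight 0.18 + 0.82 × 10/30 ≈ 0.46; ratio ≈ 0.40, well above 0.25.
- Even deaths: 0.25 × 10/30 = 0.083; weight 0.083 + 0.917 × 10/30 = 0.389; ratio 0.21.

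So under early deaths part of the apparent saving is upward bias. At a true mortality of exactly 15% with front-loaded deaths and 15–25 transplants a month, the chance of stopping is 7–10% with all recipients and 22–27% with weighting.

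**6. Other denominators.**

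- Deaths plus completers stops 2–19% of trials at a true 5% and 24–76% at a true 15% (5–20 per 30 days), so it is not a usable default.
- A matured cohort alone (only recipients transplanted at least 30 days earlier, for both deaths and n) is a fair estimate but discards known early deaths. Its within-trial median against all recipients ranges from 11 transplants later to 7 earlier. At 40% mortality, early deaths and 20 per 30 days, median transplants at stopping are 32 against 22.
- The present rule plus a matured-cohort check, stopping if either triggers, cannot stop later than the present rule. At 25% mortality and 8–25 a month it stops a mean of about 5–25 transplants earlier (median within-trial saving 0–9).

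**The case against.** The best defence is that n is not really undefined. The worked examples and the sentence on observed combinations point to everyone transplanted to date, and Table 1 can be used that way. The rule also does not stand alone: under Section 15.9 an independent DSMB reviews safety and can recommend termination, Section 14.2 requires deaths to be reported as soon as possible, and the DSMB charter, which is not available here, may say more. In the small-n region that Table 1 shows, one further death often closes the gap.

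Much of this stands. The all-recipients reading is the likely one, and the DSMB is a real safeguard. But that reading is the one that scores pending recipients as survivors, so settling the wording does not remove the low bias.

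A reader might go further and infer that the rule delays stopping by tens of transplants as a matter of course. The documents do not support that: they give no accrual rate and no pattern of death times. Gaps of that size appear mainly when two medians are subtracted (for example 83 against 54 at 25% mortality, even deaths and 20 per 30 days, where the median within-trial delay is 14), when the comparator is the upward-biased deaths-plus-completers count, or at the fastest accrual assumed. A reader might also infer that a simple unbiased denominator is available. Weighting is biased upward when deaths are early, and the matured cohort, used alone, can act later than the present rule.

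**Conclusion.** The point holds in a limited form. Section 10.7 monitors Day-30 survival without saying how recipients short of Day 30 are counted, and its natural reading lowers the bound and can delay stopping. The delay is skewed: small in many trials, long in a minority, and growing with accrual. The figures depend on the assumed 25% mortality, 8–25 transplants a month and the two death-time patterns; they shrink at higher mortality or slower accrual. The main effect is on when the study stops, since the chance of ever stopping by 184 recipients is nearly the same. This is a cheap improvement to a safety rule, not a defect that makes the rule unworkable.

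**What to change.** In Section 10.7:

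1. State that at each death n is all recipients transplanted to date.
2. Add a second check, made as each recipient reaches Day 30, taking both deaths and n only from recipients transplanted at least 30 days earlier. Stop if either bound exceeds the existing 15%. Level and threshold are unchanged.
3. Name the exact (Clopper-Pearson) method, which already reproduces the n = 5 and n = 10 rows of Table 1.
4. Show operating characteristics at the accrual the sponsor expects.

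The cost is a few sentences, a routine calculation and a modest rise in stopping at lower mortality: from 1% or less to about 1–3% at a true 10%, and from about 3–14% to about 14–16% at a true 15%. A follow-up-weighted n would act faster. If it is preferred, its behaviour under early deaths should be shown and it should not be described as unbiased. The matured cohort should be added to the present rule and not substituted for it.
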